Nursing Home Assessments: Minimum Data Set (MDS): The MDS resident assessment instrument (RAI) is a required clinical assessment done upon admission and periodically thereafter. In this study we will use the data elements included in the MDS as independent variables designed to adjust CLC hospitalization rates and as dependent variables to insure that reductions in hospitalization don't adversely affect patient functioning. Repeated evaluations of the reliability of the MDS reveal that with proper training, 92% of the identification and background items are reliable with an average reliability estimate of 0.71, and all diagnoses in the MDS are reliable with an average reliability of 0.74. [24] Inter-rater reliability data on over 6000 residents drawn from 209 facilities in 10 states were assembled on 100 different MDS data elements, average Kappa values exceeded .7 in over 90% of the items. The validity and reliability of summary scales measuring dependence in physical and cognitive functioning, mood, etc. have been documented in comparison with research instruments and other criteria. [25-34]

As of January 1st, 2012 VA CLCs began using the MDS 3.0 as the required resident assessment instrument. Psychometric analyses done as part of the developmental work and field testing of the MDS 3.0 reveal excellent inter-rater reliability for the new item definitions and many of those measuring function were not changed from the MDS 2.0. [name], one of the investigators in this project, was the architect of the MDS 3.0 so we are confident that we'll be in a position to work effectively with these data.[35, 36]

Facility Level Data: Facility information on CLCs is constructed by aggregating MDS and VA as well as Medicare claims and utilization data based upon Veterans' location. Specifically, we will create facility level aggregate measures of hospitalizations from a CLC as well as the proportion of short and long stay residents in the facility and the proportion of residents with primary psychiatric diagnoses. Finally, geographic proximity to the VAMC inpatient unit will be obtained from GEC as part of the CLC matching process.

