the CLC in a month per person year at risk of hospitalization in that month. This measure has been constructed per CLC using VHA-Medicare merged data from 2004 and afterwards obtained under [name] current HSR&D IIR. The measure will be constructed covering the period from at least the 24 months preceding the introduction of the INTERACT program until 24 months after the introduction of the INTERACT program. Since hospitalization rates vary substantially during flu season, we have fit an ARIMA model to reduce the heterogeneity of variance in this monthly measure of hospitalization, thereby reducing the heterogeneity of residual variance. An ARIMA model will be fit for each CLC in the study, then using the monthly difference between the observed to the expected value to compare between any two matched CLCs over time. The dependent measure is a facility aggregate which we will risk adjust using indirect standardization by stratifying the per CLC month measure separately for long stay and short stay person months at risk of hospitalization. [See the Statistical Considerations section below for a detailed presentation of the ARIMA model.]

[figure not shown]

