An alternate version of the outcome is a ***per-person, risk adjusted, probability of hospitalization*** variable which will be calculated and compared across intervention and control CLC pairs. In 2007, 32% of Veteran's were hospitalized at any time during the course of the year, ranging from under 10% per CLC to nearly 50%. However, since each Veteran had a different number of person months of observation, something that varies across CLCs, these individual probabilities will be examined separately for short and long stay patients. For short stay patients, we'll calculate the proportion with a 30 day re-hospitalization, adjusting for patient characteristics on the admission MDS and the originating hospital diagnosis and length of stay. For long stay residents (those who are residents of a CLC for at least 100 days), we will calculate the likelihood of hospitalization over a 6 month period, adjusting for MDS measured clinical and functional characteristics relying upon the MDS assessment closest to the beginning of the 6 month period. Both of these measures have been extensively used in the literature using Medicare fee for service claims and have been used by [name] and his colleagues at Brown in preparing these measures for use in the Commonwealth Scorecard system to rate states' health care system.[2][[37]]

The underlying intent of the intervention is to decrease transfers by avoiding decline, appropriately managing acute change or decline in the CLC, and improving the use of advance care plans. Transfer rates alone do not tell us whether these kinds of changes occurred in association with the focused intention of the intervention, i.e. to reduce the rate of potentially avoidable hospitalizations. We will therefore also examine the overall rates of ***potentially avoidable and inappropriate transfers*** prior to the intervention compared to these rates during the consolidation phase of the intervention (among only the CLCs exposed to the INTERACT program), using a tested and reliable structured implicit review process. The Structured Implicit Review (SIR) yields numerous judgments about the need for transferring the Veteran to the hospital and attributes this decision to whether identifiable clinical care problems had been missed and the expected benefits of hospitalization. The final outcome variable is an ordinal variable ranking the hospitalization in terms of the degree of "avoidability".

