Using the results of the Structured Implicit Review process, we will determine the percent of hospital transfers rated as avoidable through better quality of preventive care and early change recognition and the percent rated as inappropriate because the Veteran’s condition could have been safely managed in an average VA CLC. We will compare the percentage hospitalized before the implementation to that after implementation. The sample size of 326 hospitalization records, 163 pre and 163 post-INTERACT, is based upon the assumption that the pre-intervention rate of potentially avoidable hospitalizations will be 40%. For the overall project, we are hypothesizing that there will be a 20% reduction in hospitalizations. Logically, the reductions in hospitalizations will come primarily from the "avoidable" type (otherwise we have a causal inconsistency). Thus, if 40 of 100 hospitalizations pre INTERACT are avoidable and all of the 20% reduction in hospitalizations (20 of 100) will come from among those that are avoidable, we expect a 50% reduction in the rate of avoidable hospitalizations. So, if the pre rate is 40% and the post rate is 20%, using a one tailed test at the alpha .05 level, we need about 100 records

before and 100 after to achieve a power of .90. In the event that some "unavoidable" hospitalizations are really avoided due to the intervention, we increase the sample size to 163 per time period.

Finally, we will test for unintended consequences by examining changes in the rates of overall mortality and in the rate of decline in the late loss ADLs, as measured by the MDS 3.0 nursing home resident assessment, which is done upon admission, periodically thereafter and upon discharge.[45]

Random selection of records with a transfer: A total of 326 medical records with a transfer to the hospital and across the eight intervention CLC sites will be reviewed, 163 pre-INTERACT intervention and 163 post-intervention.

The 163 pre-INTERACT records will be selected from a list of transfers that occurred during the 18 months prior to INTERACT being introduced to the CLCs. This list will be compiled by the study programmer/analysts who will pull it from current CDW data and MDS data. Once the list is generated, random selection will occur to obtain 163 records pre-intervention.

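### The alternate long-stay outcome is adjusted for the MDS assessment nearest the start of the 6-month period, so the assessment can postdate the hospitalization being modelled

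*Combined protocol and SAP*

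**What the plan says.** Outcome Measures introduces the person-level measure with the words "An alternate version of the outcome is a" and goes on to a per-person, risk-adjusted probability of hospitalization, handled separately for two groups.

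- **Long stay**, defined as "those who are residents of a CLC for at least 100 days": "we will calculate the likelihood of hospitalization over a 6 month period", with adjustment for MDS clinical and functional items, "relying upon the MDS assessment closest to the beginning of the 6 month period".
- **Short stay**: 30-day re-hospitalization, "adjusting for patient characteristics on the admission MDS" together with the originating hospital diagnosis and length of stay.

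On when assessments take place, the data-source description of the MDS says that it "is a required clinical assessment done upon admission and periodically thereafter". Aim #4, when it discusses unintended consequences, adds discharge: "which is done upon admission, periodically thereafter and upon discharge". No interval is given.

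Aim #4 also says how the person-level measure is analysed: an approach like that for the primary outcome, which is difference-in-difference against matched controls, with the resident as the unit and standard errors clustered by facility. It puts no limit on which assessment may be used.

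**The concern.** A risk adjuster should describe the resident before the period in which the outcome can occur. The long-stay rule does not secure this. An assessment 20 days after the start is preferred to one 40 days before it, even if the resident was hospitalized on day 10.

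Three things follow.

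1. Function recorded after a hospital stay partly reflects that stay. Using it as a baseline risk factor conditions on a consequence of the outcome.
2. INTERACT is meant to work partly by preventing decline, and ADL decline is itself examined under Aim #4. Function measured inside a post-implementation window may lie on the path from intervention to outcome.
3. If a transfer to hospital produces a discharge assessment, hospitalized residents will more often have an in-window assessment than the rest. The timing of the covariate then depends on the outcome.

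At stake is the long-stay half of the alternate outcome. The primary monthly rate is adjusted in another way: the plan will "risk adjust using indirect standardization by stratifying the per CLC month measure separately for long stay and short stay person months", and no resident-level MDS covariate enters.

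**Working it through.** **Is the rule really open?** Four places bear on it. Outcome Measures gives the nearest-assessment rule for long stay. The same section ties short stay to the admission MDS, so timing is fixed for one group and left open for the other. The MDS data-source paragraph and Aim #4 together place assessments at admission, at intervals and at discharge, so some will fall inside a 6-month window. The Aim #4 analysis text adds no restriction. The rule is therefore two-sided as written.

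**How many residents could be affected?** The plan states no figure on this, so there is nothing to reproduce. What follows is an illustration.

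Inputs:
- Interval between assessments, L: assumed 30 to 180 days (not in the documents).
- Period start: assumed uniform within the interval.
- Time to first hospitalization: assumed exponential with rate λ over a 182.5-day window.
- Low rate: 25% hospitalized in 6 months, the community nursing home figure in the Introduction/Background. λ = −ln(0.75)/182.5 = 0.001576 per day, P = 0.25.
- High rate: 1.3 per person-year, from Preliminary Studies. λ = 1.3/365 = 0.003562 per day, P = 1 − exp(−0.65) = 0.478. This covers all CLC residents and lies outside the range of 0.1 to 1.1 printed beside it, so it serves only as an upper value.

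*(a) Scheduled assessments only.* The next assessment is nearer than the last one with probability 0.5, whatever L is. When it is, the delay is uniform on 0 to L/2. With x = λL/2, the share of hospitalized residents whose assessment follows the event is

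½ × [1 − (1 − e^(−x))/x] / P.

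At L = 90 and the low rate: x = 0.0709, the bracket is 0.0346, and ½ × 0.0346/0.25 = 0.069. At the high rate: x = 0.1603, the bracket is 0.0760, and ½ × 0.0760/0.478 = 0.080.

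*(b) A transfer also triggers an assessment.* This assumes that the discharge assessment covers hospital transfers, which the documents do not say. An event nearer to the start than either scheduled assessment now supplies the covariate. The share is [1 − (1 − e^(−x))/x] / P, twice that in (a).

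| L (days) | (a) scheduled only | (b) transfer-triggered |
|---|---|---|
| 30 | 2–3% | 5–6% |
| 60 | 5% | 9–11% |
| 90 | 7–8% | 14–16% |
| 120 | 9–10% | 18–21% |
| 180 | 14–15% | 27–30% |

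Each range runs from the low rate to the high rate. A simulation of 1,000,000 residents per setting agrees with the formulas.

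*Dependence of timing on outcome.* In (b) at L = 90, 57–58% of hospitalized residents have a post-start assessment, against 50% of those not hospitalized. In (a) the share is 50% in both groups.

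**After the change.** With an on-or-before rule, no adjustment assessment follows the start or the event, by construction. At L = 90 the mean age of the covariate rises from 22.5 days (L/4, either side of the start) to 45 days (L/2, always before). No sample size or power figure depends on this rule.

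**The case against.** The strongest reply is that this is loose wording on a subsidiary measure. The short-stay model is anchored at admission, which suggests that baseline adjustment was intended throughout, and Outcome Measures says that both measures are in established use. The same rule would also apply in both arms and both periods, so a difference-in-difference comparison may cancel much of the distortion.

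Much of this stands. Intent may well have been a prior assessment, but an analyst following the text would do otherwise. Established use does not settle timing for a treatment comparison. Cancellation is plausible, but it need not be complete if in-window function or transfer patterns change with INTERACT.

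A reader might infer more than the documents support:

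- *That the main result is at risk.* The primary outcome is also called risk adjusted, but by stratification on length of stay, without resident-level MDS covariates.
- *That the shares above measure bias, or show it to be small.* They count residents. No bias in the treatment comparison has been computed.
- *That residents who leave during the window have only earlier assessments.* Aim #4 says that the MDS is done at discharge, so leavers would normally have an in-window one. For deaths the documents are silent.
- *That an on-or-before rule removes all adjustment for treated function.* Follow-up runs to 24 months after introduction. In a window that starts well into that time, the last prior assessment was itself made under INTERACT.

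**Conclusion.** The point holds for the long-stay part of the alternate per-person outcome. The stated rule permits, and for about half of residents would select, an assessment made after the window opens. That half rests on evenly spaced assessments with a random start. Among hospitalized residents, the share adjusted on a post-event assessment is about 2–15% with scheduled assessments only and about 5–30% if transfers trigger one, over assumed intervals of 30 to 180 days. The direction and size of any resulting bias are unknown, and some of it may cancel between arms and periods. This is a minor but worthwhile correction. The primary analysis, sample size and power are unaffected.

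**What to change.** In Outcome Measures, replace the nearest-assessment rule for long-stay residents with the most recent MDS assessment on or before day 1 of the 6-month period, within a stated maximum look-back. Keep residents who have no qualifying assessment in the analysis with a missing-covariate indicator, since Patient Selection expects to exclude no Veterans.

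The 100-day definition means that an earlier record will normally exist, so no new data are needed. The change is cheap but not free: covariates become somewhat older, about 45 days on average instead of 22.5 at an assumed 90-day interval.

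The change ends after-event adjustment only. For windows that start after implementation, a sensitivity analysis restricted to pre-intervention or non-modifiable covariates could be added, to show whether adjusting for function already influenced by INTERACT changes the estimate.

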Hospitalizations can be loosely classified into those that are potentially avoidable versus unavoidable.[5, 18, 19] Some hospitalizations may be seen as avoidable because the underlying event is avoidable with proper care of a chronic condition. For example, hospitalizations related to diabetes, heart failure (HF), and chronic obstructive pulmonary disease (COPD) could be avoided if proper diet, exercise, and medication management are maintained. A separate but related distinction can be made between hospitalizations that are discretionary versus nondiscretionary, once an adverse health event has occurred.[5, 18] While hospitalization is seen as always necessary for some acute conditions such as hip fracture, transfer to a hospital is discretionary for other conditions such as pneumonia and dehydration. In the discretionary cases, the decision to hospitalize may depend on resources available in the LTC setting and family preferences as well as patients' clinical status.[20] Reducing hospitalizations is most feasible among avoidable and/or discretionary events.

A recent report from the Research Triangle Institute examined the dually eligible (Medicare and Medicaid) population in community NHs and found that more than one-third of these dually eligible beneficiaries were hospitalized at least once, totaling almost 1 million hospitalizations per year.[21] Of these, 382,846, or 39%, may have been avoidable, either because the condition might have been prevented or because the condition might have been treated in a lower level of care setting than a hospital. These potentially avoidable hospitalizations include 241,000 hospitalizations (63%) originating from a Medicaid-covered NH stay, 73,000 (19%) from a Medicare-covered SNF stay. In both Medicare covered SNF stays and Medicaid covered nursing facility stays, pneumonia accounted for over 30% of potentially avoidable hospitalizations.

To our knowledge no comparable hospitalization data exist on Veterans receiving post-acute care (PAC), approximately ½ of the CLC population. In community NHs, re-hospitalization of short stay, PAC patients is increasingly recognized as a major issue; however, these rates may differ between community NHs

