VHA Utilization and Costs: VA utilization will be obtained from the national automated datasets maintained at the Austin Automation Center. The VHA Medical SAS Datasets are national administrative data for VHA-provided health care utilized primarily by Veterans. The datasets are provided in SAS format by fiscal year (Oct. 1 - Sept. 30). These data are extracted from the National Patient Care Database (NPCD). Two particular datasets will be used: the “Bed Section” dataset for acute and extended (nursing home) utilization. The “Bed Section” files (as opposed to the Main files) will allow us to differentiate between acute hospitalizations and inpatient rehabilitation, which is necessary for the creation of the Residential History File (see below) as well. These datasets will be used to obtain specific dates of admission and discharge that will enable us to define study outcomes. They also contain variables describing patient demographics, primary/secondary diagnosis, length-of-stay and up to 10 diagnostic code variables per admission. In conjunction with [name] and staff at HERC (Health Economic & Resource Center) we will use HERC cost data based upon standardized cost accounting rules.

Medicare Claims: Medicare data for Veterans are available to VA researchers with approved projects. The VA Information Resource Center, VIREC, prepares the data and attaches it to VA's Scrambled Social Security Numbers, which allows researchers to link VA and Medicare healthcare utilization data. The data are distributed to VA researchers as SAS datasets. The VIREC cohort, first
Version 14: 06/28/17 VA Central IRB Protocol Page 5 of 43
Amendment 15

constructed for 1999, included a total of 6.4 million Veterans. Of these, there were approximately 6.1 million Veterans who were alive as of January 1, 1999. This cohort definition is updated annually to include the most recent source files to produce a cumulative finder file. Currently, files include claims from 1999 through 2011, and are updated continually.

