Once CLCs are matched, the randomly selected CLC will be approached to solicit their participation with the strong endorsement of GEC leadership. We will approach the randomly selected experimental CLCs until up to 15 have agreed. If a CLC declines to participate, both members of the pair of matched CLCs will be dropped from consideration. The matched “control” case of those CLCs that agree to participate in the INTERACT program will not be approached. The “control” status of a CLC will be known to no one outside of the project research team and will not be divulged in any project description or publication.

Patient Selection: We do not anticipate excluding any Veterans in CLCs from the population to be included in the outcome analyses. The CLC is the unit of random assignment, meaning the intervention changes the skills of CLC staff. For each CLC agreeing to adopt the INTERACT program, it will be as if the CLC is introducing a focused quality improvement program to their staff. As such, no individual patient consent will be requested. We will separately examine hospitalization rates of Veterans classified as long stay or short stay based upon the pattern of recent admission and discharge data, but this will be regardless of their clinical condition or diagnoses.

Outcome Measures: The primary outcome (on which our statistical power estimates were based) will be the **overall hospitalization rate** calculated as the number of admissions to hospital from

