Between sessions, suggested implementation activities will include practicing the use of the tools and tracking acute care transfer and hospitalization rates using existing information systems in the CLC, either paper or electronic formats. Teleconferences will be held every other week and include opportunities for participating CLCs to ask questions, discuss implementation challenges, and share successes with other CLCs. Individual CLC calls as well as calls with multiple intervention CLCs (Cohort calls) implementing INTERACT at the same time will be held. The calls will include the Champions and key leadership staff at the CLC.

The subsequent 12-18 month period will be characterized by every other week conference calls. The goal is to keep Champions and CLC staff engaged in the ongoing quality improvement process designed to reduce hospitalizations. Calls will be with the Champions and will focus on CLC staff experiences using the INTERACT tools, particularly those related to documenting the reasons for hospitalization.

The INTERACT Tools: The INTERACT tools were developed and refined with extensive input from national experts in nursing home care, as well as from all levels of direct care NH staff and medical providers. The tools are consistent with evidence-based and expert recommended clinical practice guidelines.[40-43]

There are four types of tools within the INTERACT QI program, illustrated in the figure above:

1. Communication tools: structured to document communication between nursing assistants and licensed nurses (RNs/LPNs/LVNs), between nurses and medical providers (MD, NP, PA), and between CLCs and hospitals. These tools include an Early Warning Tool (“Stop and Watch”), **S**ituation **B**ackground **A**ssessment **R**equest (“SBAR”) Communication Form and Progress Note, Acute Care Transfer Checklist, CLC to Hospital Transfer Data List, Hospital to CLC Transfer Data List, and CLC Capabilities List.

2. Decisions Support Tools: including change in condition file cards and care paths for ten conditions that are common causes of potentially avoidable hospitalization of Veterans in CLCs including acute mental status change, change in behavior with new or worsening behavioral symptoms, dehydration, falls, fever, GI symptoms such as nausea, vomiting and diarrhea, shortness of breath, symptoms of CHF, lower respiratory illness and symptoms of UTI.

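### Avoidable hospitalizations, the stated target of INTERACT, are never compared between randomised arms, although diagnosis codes held for both arms would support a secondary targeted rate

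*Combined protocol and SAP*

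**What the plan says.** **Between-arm measures.** Under Outcome Measures, the primary outcome is the overall hospitalization rate, "calculated as the number of admissions to hospital from" the CLC in a month per person-year at risk. The alternate outcome is a risk-adjusted probability: 30-day re-hospitalization for short-stay Veterans and any hospitalization over 6 months for long-stay Veterans. Diagnosis enters only as an adjustment variable. Aim #4 analyses these measures by difference in difference against the paired CLC.

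**Avoidability.** Outcome Measures then states: "Transfer rates alone do not tell us whether these kinds of changes occurred in association with the focused intention of the intervention". The remedy it gives is the SIR, restricted to CLCs exposed to INTERACT. Aim #4 samples 163 transfers before and 163 after, all from intervention sites.

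**Where the effect is expected.** The Introduction says: "Reducing hospitalizations is most feasible among avoidable and/or discretionary events". The SIR sample-size text in Aim #4 says that "the reductions in hospitalizations will come primarily from the" avoidable type, takes 40 of 100 pre-intervention admissions as avoidable, and in its arithmetic draws all 20 averted admissions from those 40. The INTERACT Tools section describes "care paths for ten conditions that are common causes of potentially avoidable hospitalization of Veterans in CLCs".

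**Data held.** Of the VA files, the VHA Utilization and Costs section says: "They also contain variables describing patient demographics, primary/secondary diagnosis, length-of-stay and up to 10 diagnostic code variables per admission". The Medicare Claims section lists DRG and multiple diagnoses per hospitalization. The Study Procedures overview says that control-site outcomes come only from existing data, so the same fields are available for controls.

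**The concern.** Aim #4 asks two questions: did hospitalizations fall relative to matched controls, and did avoidable hospitalizations fall? Only the first uses the controls. The second rests on an uncontrolled before/after comparison, and the Limitations section can only assume that no competing forces, such as policy changes, were at work. If the avoidable share fell across all CLCs over the same years, the SIR would show a fall that INTERACT did not cause.

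The converse also matters. If the all-cause result is flat or modest, no between-arm evidence would show whether an effect was present in the targeted type of admission and masked by the rest. Unless a targeted rate is defined beforehand, any between-arm look at admission types will be post hoc.

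**Working it through.** **1. Which measures use controls, and which address avoidability**

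| Measure | Control CLCs used? | Specific to avoidable stays? |
|---|---|---|
| Monthly hospitalization rate (primary) | Yes | No |
| 30-day and 6-month probabilities | Yes | No |
| SIR avoidability rating | No | Yes |

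No row has yes in both columns.

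**2. The plan's own figure.** For 40% versus 20%, one-sided 0.05, power 0.90, the pooled two-proportion formula gives 89 records per period, or 98 with continuity correction. This agrees with the stated figure of about 100. So the 40/60 split is a planning assumption for reviewer-judged avoidability, and it reproduces as such.

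**3. What the split implies for the all-cause rate.** Use signal-to-noise = (difference in counts)/√(sum of counts), per 100 control admissions, with all averted stays avoidable.
- 20% reduction: all-cause 20/√(100+80) = 1.49; avoidable only 20/√(40+20) = 2.58; ratio 1.73.
- 10% reduction: all-cause 10/√(100+90) = 0.725; avoidable only 10/√(40+30) = 1.195; ratio 1.65.

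**4. Power at a 10% reduction.** Statistical Considerations gives 0.77 for 8 CLCs (printed as .77%). The simulation parameters and test level are not given, so I take 0.77 as stated and assume a two-sided 0.05 test. The noncentrality is 1.96 + 0.74 = 2.70. Let f be the share of all admissions on the list and g the share of averted admissions on it. The relative effect grows by g/f and its relative standard error by 1/√f, so the test statistic is multiplied by g/√f. This is slightly more conservative than step 3: 1/√0.40 = 1.58 against 1.65. Power is Φ(2.70·g/√f − 1.96).

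| f | g | g/√f | Power |
|---|---|---|---|
| 0.40 | 1.00 | 1.58 | 0.99 |
| 0.40 | 0.80 | 1.26 | 0.93 |
| 0.40 | 0.70 | 1.11 | 0.85 |
| 0.40 | 0.40 (even fall) | 0.63 | 0.40 |
| 0.60 | 1.00 | 1.29 | 0.94 |
| 0.60 | 0.80 | 1.03 | 0.80 |
| 0.60 | 0.70 | 0.90 | 0.68 |

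Break-even is g = √f: 63% at f = 0.40 and 77% at f = 0.60. The f = 0.60 rows are an assumption. They are shown because the Introduction says that most hospitalizations involve a short list of condition groups.

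**5. Imperfect codes.** The documents give no accuracy of codes against SIR judgement. Take sensitivity = specificity (assumed), 40% truly avoidable, all averted stays avoidable and a 10% reduction. With the step 3 formula, power is 0.96–0.97 at 0.90, 0.90–0.91 at 0.80, about 0.80 at 0.70, and 0.65–0.67 at 0.60. Ranges cover one- and two-sided tests. The gain is gone slightly below 0.70.

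**6. The 20% design effect.** Stated power for 8 CLCs at variance factor 1.0 is already 0.99, so a ratio of 1.73 adds almost nothing.

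**7. Sparsity.** Assume a full 50-bed CLC (the minimum size for matching) at the 1.3 hospitalizations per person-year in Preliminary Studies: 50 × 1.3/12 = 5.4 admissions a month, of which 40% is 2.2. The same sentence gives a highest rate of 1.1, so 1.3 is uncertain; at 1.1 the figures are 4.6 and 1.8. A quarter at 1.3 holds about 6.5 listed admissions.

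**The case against.** **The plan has a remedy.** The sentence after the one quoted from Outcome Measures introduces the SIR. The protocol's reason for it is sound: avoidability needs clinical synthesis that coded data may not support. Charts from both periods are mixed, and reviewers are told neither the period nor the intervention. This stands as a reason to keep the SIR. It protects the ratings from bias but does not supply a control group.

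**Not every between-arm outcome counts admissions.** Mortality is charted against paired facilities, ADL decline is tested, and Aim #5 compares costs and considers types of hospitalization. The point is therefore confined to hospitalization rates and probabilities.

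**The other 60% is not simply noise.** A reader might infer this from the 40-of-100 arithmetic. The documents do not support it: Aim #4 says primarily, and it enlarges the SIR sample in case some unavoidable stays are averted. Advance care planning, the third core strategy, is not tied to any diagnosis.

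**The Patient Selection wording proves little.** The phrase "regardless of their clinical condition or diagnoses" concerns which Veterans are included, not which admissions are counted. The point rests on the outcome definitions.

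**No ready-made list supplies 40%.** The care-path conditions are largely presenting signs, with no mapping to discharge diagnoses. Falls are among them, while the Introduction treats hip fracture as always needing hospital. The 39% cited there comes from dually eligible residents of community nursing homes. These objections stand and limit any claim about power.

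**All-cause suits the primary.** It matches the first question of Aim #4 and the budget aim, and does not depend on coding practice. Accepted; nothing here displaces it.

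**Conclusion.** The point holds in this form: the randomised design is never applied to avoidable hospitalizations, although the plan names them as its target and holds the data to do so. The consequence is interpretive. The SIR cannot separate secular change from an intervention effect, and the between-arm rates cannot show which kind of admission changed.

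It should not be read as showing that the trial is underpowered. At the expected 20% reduction, stated power is 0.99. At 10%, a targeted rate could raise 0.77 to about 0.99 or lower it to about 0.40, depending on how much of the reduction falls on the list and how well codes identify avoidable stays. Neither is known from the documents. These figures also assume count-like noise and accept the plan's 0.77; over-dispersion would change them. Nor would a null all-cause result be uninterpretable, since the SIR would still give some evidence, though uncontrolled.

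This is a worthwhile, inexpensive improvement, not a flaw in the primary analysis.

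**What to change.** Keep the all-cause rate as primary and keep the SIR. In Outcome Measures and Aim #4, add one pre-specified secondary between-arm outcome: the rate of admissions from the CLC whose diagnosis is on a fixed list of potentially avoidable codes.

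- Fix the list, and which diagnosis field is used, before outcomes are compared by arm. Apply both identically to VA and Medicare records, to both arms and to both periods.
- Use the same pair-matched difference in difference. Aggregate to quarters or longer if monthly counts are too sparse for CLC-level ARIMA models, and state that rule beforehand.
- Report the rate for all other admissions beside it as a comparison series. It is not a pure negative control, because the plan allows some of those stays to be averted.

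Cost: protocol wording, a code list and an additional analysis, with some adaptation of the time-series step. No new data are needed. The downsides are that codes classify avoidability imperfectly and that there is one more secondary outcome to interpret.
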